8.2.2 No Response

No response to chemotherapy will be defined as meeting at least one of the criteria below:

A. Pre-excision MRI reporting at least one of these findings:

- cT3^{ab} stage
- node positive disease
- not clear circumferential radial margin (CRM)

OR

B. Excision specimen reporting at least one of these findings:

- node positive disease
- ypT2
- ypT1 tumours with:
 - poorly differentiated histology, and/or
 - lymphovascular invasion, and/or
 - positive margin within <1mm.

8.3 Organ Preservation Rate

Organ preservation rate is defined as the proportion of patients who avoid TME.

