13.2 Endpoints and Analysis

The primary endpoint of this study is the protocol specified organ preservation rate, defined as the proportion of patients with tumour downstaging to $ypT0/T1^{good}$ N0 and who avoid radical surgery. The 95% confidence interval for the organ preservation rate will be calculated.

The 3 year locoregional relapse rate, distant relapse rate, and disease free survival will be estimated based on Kaplan-Meier method.

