13.3 Sample Size and Duration of Study

Prospective phase II studies have documented an organ preservation rate of 50-68% among patients with clinical T1-3N0 rectal tumours treated with chemoradiation and minimally invasive surgery.

Based on these historic phase II data, the experimental treatment would be considered of no interest if the protocol specified organ preservation rate is 50% or lower (H_0) and as promising if its avoidance rate is 65% or higher (H_1). With an optimal two-stage minimax design, 22 patients would be accrued in the first stage.

The trial would be stopped at the end of the first stage if the number of patients who avoided radical surgery is 10 or less. Otherwise the trial would proceed to the second stage to accrue 28 additional patients. The experimental procedure would be considered as promising if, out of the total patients accrued, 30 or more patients avoided radical surgery. The exact type I error rate and power of this design are respectively 0.1 and 0.8. The minimum and maximum sample sizes are respectively 22 and 50 evaluable patients. Allowing for a 15% inevaluable rate, the total sample size is 58 patients.

The interim analysis at 22 patients will also determine if the trial has recruited a proportional representation of T1/2 and T3 patients. If the interim analysis shows disproportionality between the number of T1/2 and T3 patients, the eligibility criteria and reasons limiting enrollment will be reviewed and the trial team will consider extending accrual of one or the other group if it is determined to be necessary.

If the avoidance rate of the proposed procedure is 50% or lower, there is a 42% chance this study would be stopped.

Based on CCTG previous survey results, the study potentially opening at 12 centres, each centre accruing 3 patients per year, the estimated minimum accrual time for 58 patients is 19 months.

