2.2 Study Design

CO.28 is a single arm, two-stage phase II clinical study of FOLFOX/CAPOX as a neoadjuvant treatment for patients with stage I-II (cT1-3ab/N0) rectal cancer. The study is being conducted by the Canadian Cancer Trials Group.

A total of 50 evaluable patients would be enrolled, in a two-stage minimax design with 22 patients accrued in the first stage. The trial would be stopped at the end of the first stage if the number of patients who avoided radical surgery is 10 or less. Otherwise the trial would proceed to the second stage to accrue 28 additional patients. Allowing for a 15% inevaluable rate, the total sample size would be 58 patients.

This study opened to accrue patients on August 22, 2017. On April 19, 2019, 11 of the 19 patients enrolled in the first stage were found to have avoided radical surgery. It was decided the study would proceed to continue accrual of patients to full sample size. The trial was closed to further accrual on May 19, 2020 after 58 patients were accrued.

A final analysis will be performed on a database which will be locked after all patients completed their treatments and all data observed from the patients are cleaned. This plan describes the details of this final analysis.

The CCTG Data and Safety Monitoring Committee (DSMC) has been reviewing safety data annually and as otherwise required. These analyses have been prepared by a CCTG/Queen's Senior Biostatistician.

3. Objectives

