7.7 Efficacy

7.7.1 Organ Preservation Rate

After completion of neoadjuvant chemotherapy, the protocol requires that patients with lesions that on pre-excision (post-chemotherapy) MRI and/or endoscopy showing evidence of progression or no response to chemotherapy to be treated with immediately

the radical TME surgery. Other patients will be treated with local excision TEMS or TAMIS. Patients with ypstage T0/T1goodN0 tumours based on local pathology ypstaging review after TEMS or TAMIS are treated with surveillance while patients with tumours with ypT2, N+ or ypT1 tumours with poor prognostic features are treated with radical TME surgery within 6-8 weeks after local excision. The numbers of enrolled patients who were treated with respectively neoadjuvant chemotherapy, TME and TEMS or TAMIS immediately after completion of neoadjuvant chemotherapy, and TME or surveillance after TEMS or TAMIS will be summarized (**Table 30**).

Organ preservation rate, the primary endpoint of this study, is defined as the proportion of patients with tumour downstaging to ypT0/T1good N0 who avoid radical surgery (TME) among all patients treated with FOLFOX or CAPOX and TEMS or TAMIS. The 95% confidence interval for the organ preservation rate will be calculated (**Table 30**).

Organ preservation rate will additionally be calculated among all patients that have received neoadjuvant chemotherapy.

7.7.2 3 Year Loco-Regional Relapse Rate

Locoregional relapse is defined as reappearance of a tumour within the rectum or pelvis. The number of patients with each site (rectum, pelvis, pelvic lymph nodes, and others) of locoregional relapse will be summarized (**Table 31**).

Locoregional relapse free survival is calculated as time from complete tumour surgical excision date (with pathology results negative for malignant disease within 1 mm of surgical margins) to the first date of definitive evidence (clinical, radiological or pathological) of locoregional relapses. Patients with distant relapse only, died, loss to follow up, or alive at clinical cut-off will be censored at respectively last date of distant relapses, date of death, date of lost to follow-up, and last disease assessment date calculated as the last of dates of attendance/last contact on Follow-up Report.

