R0		** (**)
R1		** (**)
R2		** (**)
Mesorectal excision		
Total/complete		** (**)
Incomplete		** (**)
Unknown		** (**)
Subsequent Surgery Recommended		
Not applicable (TME performed)		** (**)
Yes		** (**)
Yes, but declined by patient		** (**)
No, complete tumour resection and ypT0 or ypT1good		** (**)
Other		** (**)
Patients with definitive decision not to have tumour excision		** (**)
Reason for definitive decision not to have tumour excision		
Intercurrent Illness		** (**)
Progressive Disease		** (**)
Patient Refusal		** (**)
Death		** (**)
Other		** (**)

Table 28: Pathology Results After Surgical Treatment

Dataset: All Chemotherapy and Excision/Surgery Treated Patients

	Number of patients (%) N=**
Site of tumor	
Rectum	** (**)
Nodes	** (**)
Other	** (**)
Longest dimension of Invasive Carcinoma	
N	**
Median	**
Min – Max	** – **
Lymphatic invasion	
Yes	** (**)
No	** (**)
Not stated in the report	** (**)
Vascular invasion	
Yes	** (**)
No	** (**)
Not stated in the report	** (**)
Histology	
Adeno-carcinoma	** (**)
Squamous	** (**)
Other	** (**)
Histologic Grade	
Well -differentiated	** (**)
Moderately differentiated	** (**)
Poorly differentiated	** (**)
Undifferentiated, anaplastic	** (**)
Grade cannot be assessed	** (**)
Not stated in report	** (**)
Deepest Layer of Invasion	
Mucosa	** (**)
Lamina Propria	** (**)
Muscularis mucosa	** (**)
Submucosa	** (**)
Muscularis propria	** (**)
Serosa	** (**)
Perirectal tissue	** (**)
Subserosa	** (**)
Depth of invasion into subserosa	
Median	**
Min-max	** – **
Not Stated in Report	

Deep Margin	
Positive for invasive carcinoma	**(**)
Median	**
Min-Max	**_**
Negative	**(**)
Not stated in Report	**(**)
Not Applicable	**(**)
Mucosal Margin	**(**)
Positive for invasive carcinoma	**(**)
Median	**
Min-Max	**_**
Negative	**(**)
Not stated in Report	**(**)
Not Applicable	**(**)
Pathologic T Stage	**(**)
T0	** (**)
T1	** (**)
T2	** (**)
T3	** (**)
Unknown	** (**)
Number of Nodes examined	
N	**
Median	**
Min-Max	** - **
Number of nodes with tumour	
N	**
Median	**
Min-Max	** - **
Tumour deposits	
Yes	**(**)
No	**(**)

Table 29: Radiotherapy Treatment

Data set: All Chemotherapy & Excision Treated Patients	
	Number of patients (%) N=**
Number of Patients with Radiation treatment	** (**)
Site of Radiotherapy	
Rectum	** (**)
Sigmoid colon	** (**)
Anus	** (**)
Duration of Radiotherapy	
Median	**
Min-max	** - **
Total Dose of radiation (cGy)	
Median	**
Min-max	** - **

Table 30: Summary of Organ Preservation

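### The rule of 30 or more successes counts patients who avoid TME, while the primary endpoint also requires ypT0/T1good N0; the rule should be tied to the endpoint's numerator

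*Protocol*

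**What the plan says.** The documents describe a success in two ways.

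- **Avoiding TME only.** Protocol 8.3: "Organ preservation rate is defined as the proportion of patients who avoid TME". The final rule in Protocol 13.3, repeated in SAP section 5, calls the treatment promising if "30 or more patients avoided radical surgery". The stage 1 rule (stop at 10 or fewer of 22) is worded the same way. SAP 2.2 reports the interim in these terms: "11 of the 19 patients enrolled in the first stage were found to have avoided radical surgery".
- **ypT0/T1good N0 and no TME.** Protocol 13.2 has the endpoint "defined as the proportion of patients with tumour downstaging to" ypT0/T1good N0 and, in addition, avoidance of radical surgery. SAP 7.7.1 carries the same yp condition and sets the denominator as patients treated with chemotherapy and TEMS or TAMIS.

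Protocol 7.3 lists TME after TEMS/TAMIS for ypT2, ypT3, node-positive and poor-feature ypT1 findings. SAP Table 27 has a category for patients in whom further surgery was recommended but not accepted: "Yes, but declined by patient". Neither document says how such a patient counts for the primary endpoint or the decision rule.

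**The concern.** The two definitions agree only if every TEMS/TAMIS patient without ypT0/T1good N0 goes on to TME. A patient with, say, ypT2 who declines the operation is in the primary analysis set, counts towards the 30 under the literal rule, and is not a success under Protocol 13.2 or SAP 7.7.1.

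Every success under 13.2 also avoids TME, so the literal count can never be smaller than the endpoint count. Any discrepancy therefore runs one way, towards promising. This is the only primary endpoint, and Protocol 2.0 says that meeting it would justify a randomized trial. Which patients make up the 30 should be settled before the count is made.

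**Working it through.** **Inputs.** From Protocol 13.3 and SAP section 5: stage 1 n = 22, stop at 10 or fewer; 28 further patients; promising at 30 or more of 50; null rate 50%, alternative 65%; stated type I error 0.1, power 0.8, early stop 42% at the null. Assumed, because the documents give no value: d, the share of patients without ypT0/T1good N0 who nevertheless do not have TME, taken from 0 to 20%.

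**Step 1: reproduce the design.** With X1 ~ Bin(22, p) and X2 ~ Bin(28, p),

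P(promising) = Σ over x = 11 to 22 of P(X1 = x) × P(X2 ≥ 30 − x), and P(early stop) = P(X1 ≤ 10).

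- p = 0.50: P(promising) = 0.0977; early stop = 0.416.
- p = 0.65: P(promising) = 0.802.

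These match the stated 0.1, 42% and 0.8. The design arithmetic is sound; what is left open is what gets counted.

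**Step 2: apply the literal count when the endpoint rate is at the null.** If the true ypT0/T1good N0 rate is 0.50, the counted rate is q = 0.50 + 0.50d. Putting q into the same formula:

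| d (assumed) | q | P(promising) | P(early stop) |
|---|---|---|---|
| 0% | 0.500 | 9.8% | 41.6% |
| 5% | 0.525 | 17.3% | 32.7% |
| 10% | 0.550 | 27.8% | 24.6% |
| 15% | 0.575 | 40.7% | 17.7% |
| 20% | 0.600 | 54.8% | 12.1% |

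**Step 3: the final boundary.** A count of 30/50 = 60% (exact 95% CI 45.2 to 73.6%) is promising. If two of those 30 had an indicated TME that was not done, the endpoint count is 28/50 = 56% (41.3 to 70.0%), which is below the cut-off of 30.

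**Step 4: the interim.** The report was 11 of 19, and the rule is for 22, so 22 − 19 = 3 stage 1 patients were outstanding. If one of the 11 were reclassified, the count would be 10 of 19, and one success among the three would pass the boundary. That chance is 1 − 0.5³ = 87.5% at p = 0.50 and 1 − 0.35³ = 95.7% at p = 0.65.

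**The case against.** The strongest reply is that the phrase about avoiding radical surgery is shorthand. The null hypothesis in both documents is set on the protocol-specified organ preservation rate. Protocol 13.2 defines that term with the yp condition, and SAP 4.1 names it as the primary endpoint. SAP 7.7.1 gives the final reported rate a single numerator, and Table 30 reports only that rate, over two populations. This largely stands: the stricter definition is probably what was meant. It does not close the gap, because Protocol 8.3 is a formal definition without the condition, the alternative hypothesis is worded as an avoidance rate, and 7.7.1 never mentions the threshold of 30, which appears only in SAP section 5.

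A reader might infer more than the documents support:

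- *That the interim decision was wrong.* Nothing says that any of the 11 had an indicated TME not done, and step 4 shows that 10 of 19 is not in itself a stop.
- *That the additional all-chemotherapy rate would count unresected progression or death as organ preservation.* Protocol 8.3 alone could be read so, but SAP 7.7.1 states the yp condition before extending the rate to that population, and the analysis is supplementary.
- *That every patient who misses an indicated TME is affected.* Patients who had neither TEMS/TAMIS nor TME are outside the primary set (Protocol 8.1.1), and the stage sizes are in evaluable patients. They enter only if the rule's reference to all accrued patients is taken literally.
- *That refusal is common.* Table 27 shows that it is foreseen, not how often it happens. Eligibility requires fitness for radical surgery.
- *That Table 30 hides these patients.* It lists subsequent TME under those without ypT0/T1good N0, so the number not operated on can be found by subtraction. It does not show the reason or how they count.

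Accrual closed in May 2020, so rewording the stage 1 rule cannot change conduct. The final verdict is what can still be secured.

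**Conclusion.** The point holds as an inconsistency in the current text. The rule of 30 or more, read literally, does not use the primary endpoint's numerator. It matters for TEMS/TAMIS patients with adverse yp findings who do not have the indicated TME. At the null, the chance of a promising verdict rises from 9.8% to between 17.3% and 54.8% if 5 to 20% of patients without ypT0/T1good N0 do not have TME. That range is an assumption. If the share is zero, the two counts coincide and nothing changes.

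One related mismatch is separate. Protocol 8.2.2 part B ("Excision specimen reporting at least one of these findings") and Table 30 do not list ypT3 under excision-specimen non-response, while Protocol 7.3 lists it among the findings leading to TME. A reader might infer that this alters the success count. It does not: ypT3 is never ypT0/T1good, and avoidance of TME does not depend on the 8.2.2 label.

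**What to change.** - In SAP section 5, and in Protocol 8.3 and 13.3, count successes with the SAP 7.7.1 numerator: ypT0/T1good N0 on local pathology and no TME. A sentence in SAP section 5 applying the threshold of 30 to that count is the part that settles the verdict.
- State that TEMS/TAMIS patients with an indicated TME that was not done, for whatever reason, are failures for the endpoint.
- Add a row to Table 30 for those patients, with the reason, and report plain TME avoidance as a descriptive line.
- State which definition produced the interim 11 of 19.
- Reconcile Protocol 8.2.2 part B and Table 30 with Protocol 7.3 on ypT3.

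The cost is wording and a few table rows. Table 27 already tabulates declined surgery. Sample size and cut-offs do not change: with the single numerator the design keeps its type I error of 0.098 and power of 0.802. The downside for the sponsor is a possibly lower success count.

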8.4 Locoregional Relapse

Locoregional relapse is defined as reappearance of a tumour within the rectum or pelvis.

Evidence of Local Disease Recurrence:

- Suspicious: Suspicious imaging requiring further confirmation.
- Definite: Confirmation by cytology or histology OR Definitive imaging documenting local recurrence.

Elevated CEA only or physical examination only are not sufficient as evidence of suspicious or definite local disease recurrence.

Locoregional relapse is dated by the day of first evidence (clinical, radiological or pathological) of locoregional disease after complete tumour surgical excision date (with pathology results negative for malignant disease within 1 mm of surgical margins). It is strongly encouraged that suspicious or unequivocal evidence of first local relapse be confirmed definitively by either biopsy (preferred) or by repeat/confirmatory imaging. Where imaging evidence of first local relapse is, in the opinion of the investigator and radiologist, absolutely unequivocal and not requiring subsequent confirmation by either biopsy or follow-up imaging, this must be clearly indicated in supporting documentation.

8.5 Distant Disease

Distant disease is defined as evidence of rectal cancer disease at sites remote from the rectum.

Evidence of Distant Disease Recurrence:

- Suspicious: Suspicious imaging requiring further confirmation.
- Definite: Confirmation by cytology or histology OR Definitive imaging documenting distant recurrence.

8.6 Dating of First Recurrence

The diagnosis of recurrent disease by radiographs or scans should be dated from the date of the first suspicious record, even when the specific imaging abnormality requires subsequent confirmation by biopsy (required for confirmation of new primary malignancy) or is otherwise determined in retrospect (e.g. bone metastases that will never be biopsied but are definitively confirmed with subsequent imaging procedures).

Initial dates of first recurrence should be made as they occur by those who are responsible for the care of the patient. Dates that are based on suspicion alone will be reviewed by the CCTG coordinating office in order to establish accuracy through subsequent clinical course.

8.7 Disease Free Survival

Disease-Free Survival (DFS) is defined as the interval from complete tumour surgical excision date (with pathology results negative for malignant disease within 1 mm of surgical margins) to date of first occurrence of the events in the table below.

Patients not meeting the criteria for failure by the analysis data cutoff date will be censored at their last disease assessment date.

First Event	Disease Free Survival
None	Censored
Locoregional relapse	Failure
Distant disease	Failure
Non-protocol radiotherapy, chemotherapy or biologic therapy without documentation of the site of failure	Failure
Death due to any other reason	Failure

8.7.1 Capture of Failures and Work-up at Detection of First Failure:

Only the first event experienced will determine a patient's failure status for DFS analysis. However, in order to fully capture the patterns of failure in this study population, a detailed work-up at the time of the first failure is required, and sites of failures should be documented in the CRF.

For instance, if a patient first develops locoregional relapse, then a work-up for distant metastasis will be performed at the same time. If the distant metastatic work-up reveals the presence of distant metastasis, then all sites of failure will be documented, even though the time of the first detected failure event will be used to determine the disease free survival. Similarly, if a patient is first found to have distant metastasis, then a work-up for locoregional relapse should be performed at the same time. If the locoregional work-up does not reveal relapse at the same time, then this patient is considered to only have distant disease failure.

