A National Cancer Database study described that 17% of T2 tumours were treated with LE in 2010, of which an estimated 40% of patients received adjuvant radiation [*Stitzenberg 2013*]. The overall rate of nodal positivity in T2 tumours is reported to be 22-28% [*You 2007; Salinas 2011; Minsky 1989; Brodsky 1992*] and LE alone is not considered an acceptable standard among patients eligible for proctectomy. In CALGB 8984, 51 patients with T2 rectal tumours were treated with local excision and pelvic chemoradiation, and an 18% local relapse rate was observed [*Greenberg 2008*]. A randomized trial of 100 patients with clinical T2N0 tumours treated with chemoradiation compared subsequent modified TEMS (including significant perirectal fat/lymph node harvest) to laparoscopic TME. This RCT demonstrated pathological downstaging to ypT0/1 stage in half of patients. Rates of local and distant disease control were similar between the two arms, suggesting a combination of neoadjuvant therapy and expert TEM/TAMIS could be oncologically acceptable [*Lezoche 2012; Lezoche 2005*].

T3N0 Tumours

Standard therapy for patients with T3N0 rectal tumours is trimodality therapy with radical surgical resection plus combination 5-fluorouracil chemotherapy and external beam radiation therapy (EBRT). Patients with pathologic high-risk features are considered for post-operative chemotherapy. Retrospective case series have reported favourable outcomes among highly select groups of stage II/III rectal cancer after complete clinical response to induction therapy. Survival outcomes of patients treated with local excision after complete clinical or pathologic response (excisional biopsy) to induction chemoradiation were similar to patients treated with surgical resection [*Smith 2012; Belluco 2011; Callender 2010*]. One centre reported an actuarial local recurrence rate of 11% among 47 clinical T3, N0/N+ patients treated with full-thickness excision and EBRT. In this cohort, 49% had achieved a pCR and an additional 36% a complete clinical response after EBRT and excision. The reports have demonstrated that response to induction EBRT may be used as a means to select T3 patients for non-surgical management of rectal cancer.

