APPENDIX III - DOCUMENTATION FOR STUDY

Follow-up is required for patients from the time of enrollment and will apply to all eligible and ineligible patients. This trial will use a web-based Electronic Data Capture (EDC) system for all data collection including SAE reporting (see Section 9.0 for details regarding SAE reporting). For details about accessing the EDC system and completing the on-line Case Report Forms, please refer to the Data Management Guidebook posted on the CO.28 area of the CCTG web-site (www.ctg.queensu.ca).

The ELECTRONIC CRFs to be used in this trial are:

Electronic Case Report Form	To be Completed/Submitted Electronically:	Supporting Documentation to be sent using Supporting Document Upload Tool*
BASELINE REPORT	Due within 2 weeks of patient enrollment.	Copies of signature pages of main and optional consent forms; relevant pathology & radiology reports.
CHEMOTHERAPY REPORT	To be completed after each chemotherapy cycle. Due within 2 weeks of end of cycle. This report documents treatment, adverse events and investigations for each chemotherapy cycle.	Relevant radiology reports.
PRE-EXCISION VISIT REPORT	To be complete within 2 weeks after pre-excision visit.	Relevant radiology reports.
END OF TREATMENT REPORT	To be complete within 4 weeks after final tumour excision	
SURGERY REPORT	To be complete within 4 weeks after surgery (either TME or TEMS/TAMIS)	Relevant pathology and surgery reports.
CORRELATIVE STUDIES	See Section 12 in this protocol.	Relevant pathology reports.
FOLLOW-UP REPORT	Continued follow-up after chemotherapy, radiotherapy and/or protocol tumour excision(s) completed. Due within 2 weeks after contact with patient.	Relevant pathology, radiology and surgery reports.
RELAPSE REPORT	To be completed at the time of disease relapse or failure. Due within 2 weeks after contact with patient.	Relevant pathology, radiology and surgery reports.
SHORT FOLLOW REPORT	To be completed after disease relapse or failure and for patients that have no protocol tumour excision.	
DEATH REPORT**	Required for all patients while study is open. Due within 2 weeks of knowledge of death.	Autopsy report, if done.

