Kaplan-Meier method (**Figure 2**) will be used to estimate the 3 year loco-regional relapse rate and associated 95% confidence interval first among all patients treated with FOLFOX or CAPOX and TEMS or TAMIS (**Table 31**) and additionally among all patients that have received neoadjuvant chemotherapy.

7.7.3 3 Year Distant Relapse Rate

Distant relapse is defined as appearance of rectal cancer disease at sites remote from the rectum. The number of patients with each site of distant relapse (Lung, Liver, Brain, Distant lymph nodes, Bone, Skin, Ascites, Pleural effusion, Adrenal glands, Other) will be summarized (**Table 31**).

Distant relapse free survival is calculated as time from complete tumour surgical excision date (with pathology results negative for malignant disease within 1 mm of surgical margins) to the first date of definitive evidence (clinical, radiological or pathological) of distant relapses. Patients died, loss to follow up, or alive at clinical cut-off will be censored at respectively date of death, date of lost to follow-up, and last disease assessment date calculated as the last of dates of attendance/last contact on CRD Follow-up Report.

Kaplan-Meier method (**Figure 3**) will be used to estimate the 3 year distant relapse rate and associated 95% confidence interval first among all patients treated with FOLFOX

or CAPOX and TEMS or TAMIS (**Table 31**) and additionally among all patients that have received neoadjuvant chemotherapy.

7.7.4 3 year Disease Free Survival

Disease-Free Survival (DFS) is defined as the interval from complete tumour surgical excision date (with pathology results negative for malignant disease within 1 mm of surgical margins) to date of first occurrence of the events in the below.

- Locoregional relapse reported in CRF Relapse Report
- Distant disease reported in CRF Relapse Report
- Non-protocol radiotherapy, chemotherapy, or biologic therapy without documentation of the site of failure and reported in CRF Chemotherapy Report, Pre-Excision Report, and Surgery Report
- Death due to any other reason reported in CRF Death Report

Patients who are alive without locoregional or distant relapse or receiving non-protocol radiotherapy, chemotherapy, or biologic therapy without documentation of the site of failure at the analysis data cutoff date will be censored at their last disease assessment date calculated as the last of dates of attendance/last contact on Follow-up Report.

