7.9 Concomitant Medications and Other Anti-Cancer Treatments

Concomitant medication is defined as medication, other than protocol therapy, which is taken by patients any time on treatment or after end of treatment. Patients may also receive any other anti-cancer treatment during or after being taken off protocol treatment.

- Concomitant medications for patients during protocol treatment (reported on Chemotherapy Report, CRF Pre-Excision Report, and CRF Surgery Report) (**Table 46**)
- Concomitant medications for patients 30 days after excision (reported on CRF Follow-Up Report) (**Table 46**)
- Anti-cancer treatments for patients during protocol treatment (reported on Chemotherapy Report, CRF Pre-Excision Report, and CRF Surgery Report) (**Table 47**)
- Anti-cancer treatments for patients after protocol treatment but before relapse (reported on Follow-Up Report) (**Table 47**)
- Anti-cancer treatments for patients after relapse (reported on Short Follow-Up Report) (**Table 47**)

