At least one abnormal but all non-malignant		** (**)
All Abnormal and malignant		** (**)
Other Radiology investigations during follow-up		
All Normal		** (**)
At least one abnormal but all non-malignant		** (**)
All Abnormal and malignant		** (**)

Table 44: Transfusion

Data set: All Chemotherapy Treated Patients		Number of patients (%)
		N=**
Number (%) of patients transfused during protocol treatment		** (**)
Type of transfusion		
Number of patients received Red Blood Cells		**
Number of patients received Platelets		**
Number of patients received Other Transfusions		**
Number (%) of patients transfused during follow-up		** (**)
Type of transfusion		
Number of patients received Red Blood Cells		**
Number of patients received Platelets		**
Number of patients received Other Transfusions		**

Table 45: Major Medical Problems

Data set: All Chemotherapy Treated Patients		Number of patients (%)
		N = ***
Any major medical problem during protocol treatment		
No		** (**)
Yes		** (**)
Type of medical problem during protocol treatment*		
Medical problem A		** (**)
...		** (**)
Any major medical problem during follow-up		
No		** (**)
Yes		** (**)
Type of major medical problem during follow-up*		
Medical Problem A		** (**)
...		** (**)

* one patient may have more than one medical problem

Table 46: Concomitant Medication

Data set: All Chemotherapy Treated Patients		Number of patients (%)
		N = ***
Any concomitant medication during protocol treatment		
No		** (**)
Yes		** (**)
Type of concomitant medications during protocol treatment*		
Medication A		** (**)
...		** (**)
Any concomitant medication 30 days after excision		
No		** (**)
Yes		** (**)
Type of concomitant medications 30 days after excision *		
Medication A		** (**)
...		** (**)

* one patient may have more than one medication.

Table 47: Anti-Cancer Treatment

Data set: All Chemotherapy Treated Patients		Number of patients (%)
		N = ***
Number of patients with any other anti-cancer treatment during protocol treatment		** (**)
Chemotherapy ⁽¹⁾		** (**)
Drug 1 ...		** (**)
Radiotherapy ⁽¹⁾		** (**)
Hormonal therapy ⁽¹⁾		** (**)
Drug 1 ...		** (**)
Immunotherapy ⁽¹⁾		** (**)
Drug 1 ...		** (**)
Other ⁽¹⁾		** (**)
Drug 1 ...		** (**)
Number of patients with any anti-cancer treatment during follow-up but before relapse		** (**)
Chemotherapy ⁽¹⁾		** (**)
Drug 1 ...		** (**)
Radiotherapy ⁽¹⁾		** (**)
Hormonal therapy ⁽¹⁾		** (**)
Drug 1 ...		** (**)
Immunotherapy ⁽¹⁾		** (**)
Drug 1 ...		** (**)

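### Protocol 8.7 and SAP 7.7.4 can classify the same disease-free patient differently for DFS when adjuvant therapy follows TME, and neither rule isolates treatment given for recurrence

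*Protocol*

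**What the plan says.** The event table in protocol 8.7 makes "Non-protocol radiotherapy, chemotherapy or biologic therapy without documentation of the site of failure" a failure, on the same footing as relapse and death. Section 8.7.1 adds: "Only the first event experienced will determine a patient's failure status for DFS analysis". The protocol neither defines non-protocol therapy nor mentions adjuvant treatment in this rule.

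SAP 7.7.4 repeats the event but ties it to named forms: "Non-protocol radiotherapy, chemotherapy, or biologic therapy without documentation of the site of failure and reported in CRF Chemotherapy Report, Pre-Excision Report, and Surgery Report". The Follow-Up Report is not among them.

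SAP 7.9 assigns treatment to forms by period. The same three forms carry anti-cancer treatment during protocol treatment. The later period has its own entry: "Anti-cancer treatments for patients after protocol treatment but before relapse (reported on Follow-Up Report". Protocol Appendix III describes the Follow-Up Report in matching terms: "Continued follow-up after chemotherapy, radiotherapy and/or protocol tumour excision(s) completed". SAP Table 47 has a block headed "Number of patients with any anti-cancer treatment during follow-up but before relapse".

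The treatment plan in protocol section 7 covers pre-operative chemotherapy, excision or TME, and pelvic radiation before TME. Post-operative chemotherapy is not in it, and section 10.2 speaks only of supportive care. The background on T3N0 disease in section 2.0 notes: "Patients with pathologic high-risk features are considered for post-operative chemotherapy".

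**The concern.** The clause is useful when a patient starts new treatment because recurrence is believed to be present but no site was recorded. As worded, it does not separate that patient from one who is free of disease and receives adjuvant therapy. The second patient has no documented site of failure because there has been no failure.

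The likely setting is TME after TEMS/TAMIS for adverse pathology (rescue TME). Those patients stay in the first-listed DFS set, which is everyone given chemotherapy and TEMS/TAMIS. If adjuvant therapy counted, 3-year DFS, a secondary endpoint, would partly reflect local adjuvant practice. The extra failures would come early and would be concentrated in patients who had TME.

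The SAP's form list adds a second problem. It changes who counts as a failure without saying that this is intended.

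**Working it through.** The documents state no DFS target and no adjuvant-therapy rate, so there is no plan figure to reproduce. The check compares the two rules on the same patients and then sizes the difference.

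**Two patients under each rule**

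| Patient | Protocol 8.7, literal | SAP 7.7.4, literal |
|---|---|---|
| Margin-negative rescue TME, no disease, adjuvant chemotherapy recorded on the Follow-Up Report | Failure at start of chemotherapy | No event; form not listed |
| Complete excision, later therapy for believed recurrence, site never documented, recorded on the Follow-Up Report | Failure | No event; form not listed |

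The protocol rule counts both patients and the SAP rule counts neither. A sound rule would count only the second. DFS starts at complete excision, and the Chemotherapy and Pre-Excision Reports generally precede that date. Of the SAP's three forms, only the Surgery Report could ordinarily carry a treatment that falls after time zero.

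**Relapse rates.** Protocol 8.4 and 8.5 require reappearance of tumour or evidence of disease. SAP 7.7.2 and 7.7.3 do not list therapy as an event, and Table 31 gives it a separate line. The 3-year locoregional and distant relapse rates are the same under both rules.

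**Size under the literal protocol rule**

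Inputs:
- 50 patients, the maximum evaluable number in protocol 13.3.
- Organ preservation of 65% and 50%, the two hypotheses in 13.3. All patients without preservation are taken to have rescue TME, which is a simplification.
- Adjuvant share of 20-40% among rescue-TME patients. This is an assumption; the documents give no figure.

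Extra events = 50 × (1 − preservation rate) × adjuvant share. Fall in DFS = extra events / 50, as a simple proportion without censoring.

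| Preservation | Rescue TME | Adjuvant share | Extra events | Fall in DFS |
|---|---|---|---|---|
| 65% | 50 × 0.35 = 17.5 | 20% | 3.5 | 7 points |
| 65% | 17.5 | 40% | 7 | 14 points |
| 50% | 50 × 0.50 = 25 | 20% | 5 | 10 points |
| 50% | 25 | 40% | 10 | 20 points |

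These are upper values, because a patient who later has a true event would have failed anyway. As a check, assume 90% would otherwise be disease-free at 3 years and let the adjuvant share run from 10% to 50%:
- Lowest: 17.5 × 0.10 × 0.90 = 1.6 events, about 3 points.
- Highest: 25 × 0.50 × 0.90 = 11.3 events, about 22 points.

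**Size under the SAP's form list.** If adjuvant therapy is recorded only on the Follow-Up Report, there are no extra events and the effect is about zero.

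**The case against.** The strongest reply is that the SAP governs the final analysis, and its list of forms generally keeps adjuvant therapy out. That is correct, and it limits the practical effect. It does not settle the matter, because the SAP reaches this result through a list that also leaves out the treatment the clause is meant to catch. The Relapse Report does not close that gap: Appendix III asks for it at relapse or failure, but SAP 7.7.4 draws only locoregional and distant disease from it. Adding the Follow-Up Report without changing the definition would bring the disease-free patients in.

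A second reply is that the wording presupposes a failure whose site went unrecorded, and section 8.7.1 uses the term for places of relapse. This is a reasonable reading and probably the intended one, but neither document states it.

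A third reply is that the background sentence on post-operative chemotherapy describes standard care for T3N0 disease, not patients who have already had pre-operative FOLFOX or CAPOX. This also stands. The adjuvant share is unknown and could be small.

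Stronger readings that a reader might infer do not hold:
- *Such patients are counted as relapsed.* They are DFS failures on a separate line of Table 31.
- *Radiation before rescue TME triggers the rule.* Protocol 7.2 recommends it for ypT3+ or N+ disease, so it is protocol treatment.
- *Patients sent directly to TME after MRI add to the main figure.* They enter only the additional all-chemotherapy analysis.
- *The cost-utility model would be distorted.* Protocol 13.7 speaks only of efficacy data, and SAP 3.3 defers that plan.

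**Conclusion.** The point holds as an unresolved conflict in the DFS event definition. The protocol rule, read literally, counts disease-free patients who receive adjuvant therapy. The SAP rule, read literally, mostly does not, but it misses post-excision treatment for an undocumented failure. The two can therefore produce different 3-year DFS from one dataset.

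The difference is about 3.5-10 events in 50 patients, or up to 7-20 percentage points, if 35-50% have rescue TME and 20-40% of those receive adjuvant therapy. The second range is assumed. It would be tempting to infer that the reported DFS will be biased by that amount. The documents do not support this, because the figure belongs to the literal protocol rule and falls to about zero under the SAP's form list. The primary endpoint and both relapse rates are untouched.

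**What to change.** - In protocol 8.7 and SAP 7.7.4, define the event as non-protocol anti-cancer therapy started for suspected or confirmed recurrence whose site was not documented.
- State in both places that therapy given with no evidence of disease after complete excision or TME is not a DFS event.
- Add the Follow-Up Report to the CRF sources in SAP 7.7.4.
- List the patients treated before relapse from Table 47, and report DFS under the literal protocol rule as a sensitivity analysis.

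The cost is a short wording change in each document and one further DFS estimate. The treatments are already collected for Table 47. The drawback is that someone must classify the intent of treatment for a handful of patients. That should be done against a written rule, before the DFS results are seen.
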